# 1. Introduction

As of September 7, 2017, the dose escalation study as proposed in this protocol continues to accrue subjects at 8 mg/kg/day of anakinra as was approved by the DSMB on February 10, 2017. Thus far, anakinra has been well-tolerated and safe without any serious adverse events (SAEs) related to study drug. Throughout this protocol, this study is named "Phase I/IIa anakinra study".

Our recent work has demonstrated that the inflammasome-dependent interleukin (IL)-1 pathway is upregulated with increased transcript abundance and levels of proteins including IL-1 $\beta$  and IL-1 receptor type 1 (IL-1R1) in infants and children with acute KD.(Hoang 2014) In addition, our preliminary studies indicate that KD sera induce expression of TIFA (TNF-receptor-associated factor [TRAF]-interacting protein with a forkhead-associated [FHA] domain) in endothelial cells (ECs) (**Figure 1**). Notably, TIFA, an upstream activator of NF- $\kappa$ B through IL-1R signaling, has emerged as a key mediator in innate immunity and a likely participant in the activation of the NLRP3 (nucleotide-binding oligomerization domain, leucine rich repeat and pyrin domain containing 3) inflammasome leading to IL-1 $\beta$  production.(Ea 2004, Huang 2012, Lin 2016)

However, additional recent work by our group has demonstrated that it is not only the blocking of the IL-1 pathway that is important to prevent coronary artery abnormalities (CAA) in KD. The transformation of endothelial cells to a myofibroblast phenotype through endothelialmesenchymal transition (EndoMT) in the coronary artery wall also contributes to aneurysm formation. (Shimizu 2013) Statins, commonly prescribed as cholesterol-lowering

agents, have pleotropic effects on vascular ECs that include improving EC function, decreasing oxidative stress, and modulating innate and acquired immune responses. (Liao 2005, Oesterle 2017) Using an *in vitro* model with human ECs, we demonstrated that the krüppel-like factor 4 (KLF4)-microRNA-483 (miR-483) axis is suppressed and markers of EndoMT, including connective tissue growth factor (CTGF), are induced following incubation with sera from acute KD patients (**Figure 1**). This effect is reversed when ECs are cultured with sera from atorvastatin-treated KD patients.(He 2017) Given the pleotropic effects of statins, we conducted a Phase I/IIa, dose-escalation trial of atorvastatin for acute KD patients with early CAA (IND # 113304 held by [name] (co-I of this proposal); NCT01431105).([name] 2015) Subject accrual was recently completed for this study and atorvastatin was demonstrated to be safe and well-tolerated. In this study of children at least 2 years old, the maximum dose in the study (0.75/mg/day up to 80 mg/day) was found to be the maximum tolerated dose.

These *in vitro* data, in combination with the safety of anakinra and atorvastatin in Phase I/IIa, doseescalation studies, serve as the motivation to propose a pilot study combining anakinra at 8 mg/kg/day and atorvastatin at 0.75 mg/kg/day in children with acute KD at least 2 years old who are suffering from CAA. Throughout this protocol, this study is referred to as the "Combination therapy pilot study".

# 2. Product name

#### 2A. Product name for Phase I/IIa anakinra study

Anakinra (Kineret)

## 2B. Product names for Combination therapy pilot study

Anakinra (Kineret) Atorvastatin (Lipitor)

# 3. Chemical name

#### 3A. Chemical name for Phase I/IIa anakinra study

Recombinant-Methionyl Human Interleukin-1 Receptor Antagonist (r-metHulL-1ra)

### 3B. Chemical name for Combination therapy pilot study

Recombinant-Methionyl Human Interleukin-1 Receptor Antagonist (r-metHulL-1ra) Atorvastatin

# 4. Proposed indication

#### 4A. Proposed indication for Phase I/IIa anakinra study

Treatment of infants and children with coronary artery abnormalities from acute KD.

## 4B. Proposed indication for Combination therapy pilot study

Treatment of children with coronary artery abnormalities from acute KD.

# 5. Dosage form, route, and dosing regimen

## 5A. Dosage form, route, and dosing regimen for Phase I/IIa anakinra study

Anakinra will be administered first as an intravenous dose and then once or twice daily by subcutaneous injection following a pre-determined dose escalation protocol with three dosage levels: 4 mg/kg, 6 mg/kg, and 8 mg/kg, up to 200 mg. Once the maximum tolerated dose has been determined, the initial dose of anakinra will be given subcutaneously as with all subsequent doses.

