#### 11F. Pharmacokinetic Samples (only collected in Phase I/IIa anakinra study)

- Dosing history (dates, times and amounts of doses)
- Height and weight on day of PK sampling
- Dates and times PK samples drawn
- PK samples around initial half of the 1st dose will be drawn during the following sample windows
  - 1. 1-3 hours after the dose
  - 2. 4-6 hours after the dose
  - 3. 7-9 hours after the dose, prior to administration of the second half of the dose at 12 hours
- Trough samples 48 hours, and 2 and 6 weeks after the start of the first dose

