# **12. Dosing Protocol**

#### 12A. Dose Levels

#### 12A1. Dosing for Phase I/IIa anakinra study

All subjects will be treated with IVIG (2g/kg) and aspirin (30-50 mg/kg/day divided every 6 hours; lowered to 3-5 mg/kg/day once sent home), which is the standard of care. In order to minimize the pain from subcutaneous injections, the first two doses of anakinra have been administered intravenously and divided every 12 hours for the dose escalation part of the study (i.e. 4 mg/kg/day is 2 mg/kg every 12 hours for two doses). As has been published in the peer-reviewed literature, we administered the dose by bolus over a 1 to 3 minute period (Opal 1997). As anakinra is formulated for intravenous administration, dilution is not necessary prior to administration. The unused material is discarded in a medical waste container after each administration. See **Appendix A** for details regarding preparation of the study drug for administration of less than 20 mg.

All subsequent doses are administered subcutaneously starting 24 hours after the first dose of the medication. This study has 3 dose levels (4 mg/kg/day, 6 mg/kg/day, and 8 mg/kg/day), with a maximum dosage of 200 mg daily (**Table 5**).

If the daily dose of anakinra for a subject is  $\leq$  100mg, then the subject will receive a subcutaneous injection of anakinra once daily. If the daily dose of anakinra is greater than 100 mg (with a max dose of 200 mg daily), then the dose will be split in half with administration subcutaneously every 12 hours (i.e. a total daily dose of 150 mg will be administered as 75 mg subcutaneously every 12 hours).

Table 5. Dose Levels					
Dose Cohort	Dose Level	Number of Subjects			
1	4 mg/kg/day	3-6			
2	6 mg/kg/day	3-6			
3	8 mg/kg/day	3-6			
ТОТ	AL	9-18			

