# 16. Pharmacokinetic Analysis for Phase I/IIa anakinra study

The area under the concentration-time curve (AUC) around the first dose for anakinra will be roughly estimated as the initial concentration (the concentration extrapolated back to time zero) divided by the elimination rate, if the elimination appears first-order (log scale) or zero-order (linear scale). We will also roughly estimate the AUC using the trapezoidal rule up to the last measurable concentration. The extrapolated area after the last concentration will be estimated as  $C_{last/\lambda z}$ , where  $C_{last}$  is the last measurable concentration and  $\lambda z$  is the terminal slope of the curve. AUC from time 0 to infinity AUC0-. S calculated as AUC0-last +  $C_{last/\lambda z}$ . Noncompartmental oral clearance rate (Cl/FNC) is calculated as the ratio of dose to AUC0-. Apparent volume of distribution (Vd/FNC) is calculated as Cl/FNC over  $\lambda z$ . Half-life ( $t_{1/2}$ ) is calculated as 0.693/ $\lambda z$ . Plasma anakinra trough concentrations collected in the subacute phase (weeks 2 and 6) will be compared to the 48 hour post-dose concentration collected during the acute phase (study day 2). AUC0-, Cl/F1-C (oral clearance from 1-compartment model), and Vd/F1-C (volume of distribution from 1-compartment model) will also be determined using a 1-compartment model. This second modeling approach will be used because the data are relatively sparse for an intensive PK study, which may limit our ability to estimate every parameter for some patients.

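### The first-dose AUC rule based on back-extrapolation suits an IV bolus, but the first dose becomes subcutaneous once the MTD is set, and the PK sections are not adapted to route

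*Combined protocol and SAP*

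**What the plan says.** **Route of the first dose.** Section 12A1 records that "the first two doses of anakinra have been administered intravenously and divided every 12 hours for the dose escalation part of the study", each given as a bolus ("we administered the dose by bolus over a 1 to 3 minute period"). Section 5A changes the route after the MTD is set: "the initial dose of anakinra will be given subcutaneously as with all subsequent doses".

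**Splitting of SC doses.** Under 12A1, if the daily dose is 100 mg or less, "then the subject will receive a subcutaneous injection of anakinra once daily". Above 100 mg it is halved and given every 12 hours.

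**Sampling.** Section 11F samples around the initial half of the first dose in three windows (1-3, 4-6 and 7-9 hours). The last is timed "prior to administration of the second half of the dose at 12 hours". It does not say which subjects are sampled.

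**Analysis.** Section 16 gives three approaches, none tied to a route:
- a rough AUC from the initial concentration, meaning "the concentration extrapolated back to time zero", over the elimination rate;
- a trapezoidal AUC to the last measurable concentration, plus the last concentration over the terminal slope. Noncompartmental Cl/F, Vd/F and half-life follow from this AUC and slope;
- a 1-compartment model, with no absorption term mentioned.

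Clearance is labelled oral, although anakinra is never given orally. Section 19A promises descriptive statistics for PK variables and is silent on route.

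**The concern.** The 11F windows and the first AUC rule in Section 16 fit a split IV bolus. After an SC dose the concentration rises before it falls, so a line drawn back through the declining part meets time zero above the level that would give the true area. An analyst who applies the rule to every subject with first-dose samples would report inflated exposure for SC-first children. The IV and SC figures would differ through the method alone.

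The dose in the clearance formula raises a separate question. Depending on route and weight, a child sampled in the 11F windows has received either half or all of the daily dose, and Section 16 does not say which amount to use. Pharmacokinetics is the first secondary outcome in 7G1 and part of Specific Aim 2 in 9A.

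**Working it through.** **1. Who could be affected.** Section 12E gives 18 to 24 subjects at the MTD if the third level is reached. This reproduces: 30 - 12 = 18 and 30 - 6 = 24. Table 5 puts 3 to 6 subjects in the third escalation cohort, all IV-first. SC-first subjects therefore number from 18 - 6 = 12 to 24 - 3 = 21. Of those at the MTD that is 12/18 = 67% to 21/24 = 88%; of all 30 it is 40% to 70%.

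**2. The rule by route.** Let k be the elimination rate and ka the absorption rate.
- IV bolus: C(t) = (D/V)e^(-kt). The intercept is D/V, so C0/k = D/(Vk), which is the true AUC (ratio 1.00).
- SC, one compartment: C(t) = (FD/V) × [ka/(ka - k)] × [e^(-kt) - e^(-ka·t)], with true AUC = FD/(Vk). If every sample is in the terminal phase and ka > k, C0/k returns true AUC × ka/(ka - k), which exceeds 1. With samples in the 11F windows that condition need not hold, so I computed the fit directly.

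**3. Size at mid-window times (2, 5, 8 h).** The documents give neither ka nor k, so these are assumptions. The estimate is exp(intercept)/slope from a log-linear fit to three error-free samples, divided by true AUC:

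| Elimination half-life | ka/k = 2 | 3 | 5 | 10 |
|---|---|---|---|---|
| 2 h | 1.24 | 1.23 | 1.20 | 1.11 |
| 3 h | 1.48 | 1.24 | 1.16 | 1.10 |
| 4 h | 4.80 | 1.64 | 1.22 | 1.10 |

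Example (3 h, ka/k = 2, FD/V = 1): k = 0.2310, and concentrations are 0.4662, 0.4315 and 0.2654. The fitted slope is 0.0939 and the intercept exp(-0.5071) = 0.6022. Then 0.6022/0.0939 = 6.41, against a true AUC of 1/0.2310 = 4.33: ratio 1.48.

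The 4.80 is a corner case: the peak falls near 4 h, so the first sample is still on the rise. Fitting only the last two samples gives 1.50 there and 1.11 to 1.52 over the whole table.

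**4. Direction.** I also took elimination half-lives of 1-8 h and absorption half-lives of 0.25-8 h (928 combinations, three-point fit). The estimate exceeded true AUC in all 324 combinations with a declining fitted slope (minimum 1.04, median 1.49). In the other 604 the slope was not negative and the rule gives no value.

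**5. The trapezoid.** For SC, starting from zero at time zero and taking the terminal slope from the last two samples, the cases in step 3 give 0.79 to 1.27 times true AUC. In the example: 0.466 + 1.347 + 1.045 + 0.2654/0.1621 = 4.50, ratio 1.04. The time-zero value matters by route. For an IV bolus with a 3 h half-life and D/V = 1, concentrations are 0.630, 0.315 and 0.1575, and the area from 2 h on is 1.418 + 0.709 + 0.682 = 2.81. Starting at C0 = 1 adds 1.63 (ratio 4.44/4.33 = 1.03). Starting at zero adds 0.63 (3.44/4.33 = 0.79).

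**6. Dose amount.** 100 mg ÷ 8 mg/kg = 12.5 kg. Applying the 12A1 rule for SC doses to the first dose:
- SC-first, 12.5 kg or less: the whole daily dose before sampling;
- SC-first, above 12.5 kg: half;
- IV-first, any weight: half.

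Clearance is dose/AUC. Using D where D/2 was given doubles it; using D/2 where D was given halves it. This needs no assumed rate constant.

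**The case against.** The strongest defence is that back-extrapolation is only one of three approaches and is called rough. Noncompartmental clearance, volume and half-life rest on the trapezoid and terminal slope, so the bias does not reach them. That stands.

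Section 11F can also be read as written for IV-first subjects, because the split first dose is described for escalation. That reading is reasonable, but nothing excludes SC-first subjects, and the ambiguity itself needs settling.

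Some stronger readings are tempting and not supported:
- **That IV and SC estimates are pooled.** One clearance label and unstratified summaries suggest it, but the plan neither pools nor separates by route.
- **That the rule is wrong for most of the PK population.** The plan does not say that SC-first subjects have first-dose samples, and 40% of 30 would not be most.
- **That split doses never occur at 100 mg a day or less.** The 100 mg threshold governs SC injections. The IV first doses are split with no such condition.
- **That ka/(ka - k) gives the size of the bias.** It needs all samples in the terminal phase, which the 11F windows do not ensure.

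The consequence is bounded too: escalation, MTD and stopping rest on toxicities, and the sample size in 15A rests on transcript levels.

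**Conclusion.** The concern holds as a mismatch between a route-dependent estimator and a plan that changes route without saying so. If SC-first subjects give first-dose PK, the back-extrapolated AUC overstates exposure wherever it is computable. The direction follows from one-compartment kinetics with first-order absorption and error-free samples. The size is not fixed by the documents: about 1.1 to 4.8 times at 2, 5 and 8 h for assumed half-lives of 2-4 h and ka/k of 2-10, with the top value depending on a three-point fit. With slow absorption the rule gives no value.

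The planned trapezoidal parameters escape this bias, but they and the 1-compartment model still lack a time-zero value, an absorption term and a dose amount defined by route. The dose amount alone can shift clearance two-fold. A secondary outcome is affected; the primary safety conclusion is not. It should be corrected before first-dose PK from SC-first subjects is analysed.

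**What to change.** Reconcile sections 5A, 11F, 12A1 and 16, and state which subjects give first-dose PK. Then, in Section 16:
- restrict C0 over the elimination rate to IV-first subjects;
- for SC-first subjects, use the trapezoid from a zero concentration at time zero plus the last concentration over the terminal slope, and a 1-compartment model with first-order absorption;
- define the dose in dose/AUC as the amount actually given before the samples;
- report IV parameters (CL, V) and SC parameters (CL/F, V/F) separately, or include route in the model, and replace the oral label.

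The cost is plan wording and slightly more programming; the drawback is smaller groups per route. No change to dosing or to the sampling windows is asked for. Section 11B1 reports only 2 subjects enrolled at 8 mg/kg/day at the August 2017 revision, so the change could be made early.

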# 5B. Dosage form, route, and dosing regimen for Combination therapy pilot study

Anakinra at 8 mg/kg/day up to a maximum of 200 mg and atorvastatin at 0.75 mg/kg/day up to a maximum of 80 mg will be administered as part of a pilot study.

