#### 8C. Safety of atorvastatin in children

The safety of atorvastatin in children as young as 2 years of age with acute KD was assessed in a Phase I/IIa dose escalation study (IND 113304 issued to [name], co-investigator of this study). On May 19, 2016, the DSMB for this Phase I/IIa study evaluated the data from the Phase I dose-escalation study of atorvastatin for 6 weeks in children at least 2 years with acute KD and coronary artery damage. The DSMB determined that a 6 week course of atorvastatin was safe and well-tolerated in children  $\geq$  2 years with acute KD. In addition, based on the review of the safety of the Phase I study, the DSMB determined 0.75 mg/kg/day of atorvastatin to be the maximum tolerated dose. An additional 10 subjects were enrolled at 0.75 mg/kg/day as part of the dose expansion cohort study and further demonstrated the safety and tolerability of this dose in acute KD. The level of the cholesterol brain metabolite, 24-OH cholesterol, was measured in both statin-treated KD patients and in those treated with standard therapy for KD. No significant difference was found between the groups in the levels of 24-OH cholesterol, further demonstrating the safety of atorvastatin in acute KD as it does not reduce the levels of 24-OH cholesterol, which are important for normal brain development.

On August 1, 2017, this original Phase I/IIa dose-escalation and expansion cohort study was completed. On August 4, 2017, an annual report of the atorvastatin IND was sent to the FDA demonstrating that there had been no unexpected, adverse events in this study and that atorvastatin was safe and well-tolerated. An abstract reporting the results of the Phase I study has been accepted for poster presentation at the American Heart Association in November 2017.

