### 11B. Inclusion

#### 11B1. Inclusion for Phase I/IIa anakinra study

- Meets clinical criteria for KD according to American Heart Association guidelines (Table 4): Fever (T≥38°C or 100.4°C) ≥ 3 days and ≥ 2 clinical criteria with LAD or RCA z-score ≥ 2.5
- 2. Patient is at least 28 days old
- 3. Patient presents within the first 20 days after fever onset
- 4. Parent or legal guardian able and willing to provide informed consent
- 5. Able to be dosed between 20 mg (min amount on syringe) and 200 mg at 8 mg/kg/day

Dose escalation level*	Minimum subject weight to administer 20 mg	Maximum subject weight to administer 200 mg
8 mg/kg	2.5 kg	25 kg

\*This table includes only the 8 mg/kg dose level as enrollment in the 4 and 6 mg/kg cohorts has been completed as of the Nov 2016 revision.

\*As of the August 2017 revision, we have enrolled 2 subjects at 8mg/kg/day without any dose limiting toxicities.

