#### 11B2. Inclusion for Combination therapy pilot study

- 1. Meets clinical criteria for KD according to American Heart Association guidelines (**Table 4**): Fever (T≥38°C or 100.4°C) ≥ 3 days and ≥ 2 clinical criteria with LAD or RCA z-score ≥ 2.5
- Patient at least 2yo and weighs ≤ 25 kg (weight limit based on anakinra max dose of 200 mg/day at a calculated dose of 8 mg/kg/day)
- 3. Patient presents within the first 20 days after fever onset
- 4. Parent or legal guardian able and willing to provide informed consent

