#### 12A2. Dosing for Combination therapy pilot study

All subjects will be treated with IVIG (2g/kg) and aspirin (30-50 mg/kg/day divided every 6 hours; lowered to 3-5 mg/kg/day once sent home), which is the standard of care. Anakinra will be administered once or twice daily subcutaneously at 8 mg/kg/day with a maximum dose of 200 mg/day. If the daily dose of anakinra for a subject is  $\leq$  100mg, then the subject will receive a subcutaneous injection of anakinra once daily. If the daily dose of anakinra is greater than 100 mg (with a max dose of 200 mg daily), then the dose will be split in half with administration subcutaneously every 12 hours (i.e. a total daily dose of 150 mg will be administered as 75 mg subcutaneously every 12 hours).

Atorvastatin will be administered orally once daily at 0.75 mg/kg/day with a maximum dose of 80 mg/day.

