#### 12D. Dose Escalation for the Phase I/IIa anakinra study

The first 3 subjects in the study will be treated with 4 mg/kg/day as an IV dose of 2 mg/kg q 12 h and then as 4 mg/kg/day SQ for 2-6 weeks. If there are no dose limiting toxicities after 2-6 weeks of therapy, the safety and clinical data will be tabulated and presented to the PI, co-investigators and the Data Safety Monitoring Board (DSMB) for evaluation as to opening the next dose level (6 mg/kg) (**Tables 5 and 6**). Additional subjects will be enrolled at the highest dose if a dose limiting toxicity is not reached at 8 mg/kg/day for further study in the Phase IIa (total number of subjects is 30).

Table 6. Dose Escalation Decision Rules				
Subjects with a	Escalation Decision Rule			
DLT at a Given Dose				
0 out of 3	Enter 3 patients at the next dose level until maximum tolerated dose.			
1 out of 3	Enter a total of 6 patients at this dose level.			
	• If 0 of these additional patients experience a DLT, proceed to the			
	next dose level.			
	
 
If 1 of these additional patients experiences a DLT, then dose
 
			
	escalation is stopped (see below)			
≥ 2	At least 3 additional patients will be entered at the next lowest dose			
	level if only 3 patients were treated previously at that dose. This lower			
	dose level will be declared the MTD.			

Probability of Dose Escalation: The following probabilities of dose escalation (**Table 7**) are computed as the sum of the binomial probabilities of the following two possible outcomes that would allow dose escalation to occur: (1) no DLT observed in the first three subjects; or (2) one DLT observed in the first three subjects, followed by no DLT observed in three additional subjects at the same dose level. For example, when the underlying DLT rate is no more than 15%, the probability of dose escalation will be at least 81% or alternatively 19% probability of early study termination. Exact 95% binomial confidence intervals will be used to describe the rate of successful dose escalation.

Table 7: The probabilities for dose escalation in Phase I					
True but unknown DLT rate ≤0.1 ≤0.15 ≤0.2 ≤0.3 ≤0.4					
Probability of escalation	≥91%	≥81%	≥71%	≥49%	≥31%

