### 12E. Maximum Tolerated Dose for Phase I/IIa anakinra study

The Maximum Tolerated Dose (MTD) will be defined as the highest dose of anakinra studied at which no more than one in six patients experiences a DLT during the 6 weeks of treatment. Subjects will be enrolled at the maximum tolerated dose until a total of 30 subjects have been enrolled in the study. Given the 3+3 design of the study, if there is a DLT then a total of 6 subjects will enrolled per dose level. If we reach the 8 mg/kg/day dose level, then up to a maximum of 12 subjects will be enrolled at a dose level below the MTD (4 mg/kg and 6 mg/kg). This leaves 18 subjects treated at the MTD if the third dosing level is reached. If there are no DLTs at the first two levels, then 3 subjects will be enrolled at the MTD. Thus, between 18 and 24 subjects will be enrolled at the MTD if the 3rd dose level is reached.

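### The combination pilot fixes anakinra at 8 mg/kg/day but does not make its first dose wait until the Phase I/IIa study has cleared that level

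*Combined protocol and SAP*

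**What the plan says.** **The pilot's dose.** 5B gives the regimen as "Anakinra at 8 mg/kg/day up to a maximum of 200 mg and atorvastatin at 0.75 mg/kg/day". 12A2 repeats it: "Anakinra will be administered once or twice daily subcutaneously at 8 mg/kg/day". The 25 kg ceiling in 11B2 is derived from the same figure: "weight limit based on anakinra max dose of 200 mg/day at a calculated dose of 8 mg/kg/day". None of the three mentions a result from the other study.

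**Where 8 mg/kg stood.** A note in 11B1 records that, at the August 2017 revision, "we have enrolled 2 subjects at 8mg/kg/day without any dose limiting toxicities". Section 1, dated 7 September 2017, says the dose escalation study "continues to accrue subjects at 8 mg/kg/day of anakinra as was approved by the DSMB on February 10, 2017", with no SAE related to study drug.

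**What clears a level.** Under Table 6 in 12D a level passes with no DLT in 3 subjects, or with 1 in 3 followed by none in 3 more. 12D sends the cohort data to the investigators and the DSMB "for evaluation as to opening the next dose level". 12E says that the MTD "will be defined as the highest dose of anakinra studied at which no more than one in six patients experiences a DLT". 5A still treats the anakinra MTD as something to be determined.

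**The other drug.** In 8C, "the DSMB determined 0.75 mg/kg/day of atorvastatin to be the maximum tolerated dose", and a further 10 subjects were then treated at that dose.

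**The concern.** The two components of the regimen enter the pilot on different footings. Atorvastatin arrives at a dose that its own DSMB had declared the MTD. Anakinra arrives at a dose that its DSMB had opened for accrual, which is permission to test the level and not a finding that it is tolerated. Section 1 offers anakinra's safety record as the reason for proposing the pilot. It does not make a cleared cohort a precondition.

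Sections 11A2, 11B2, 12A2, 12F2, 15B and 20B contain no such precondition, and they do not say what the pilot would do if 8 mg/kg failed. At stake is whether a child aged 2 or over could begin two drugs together at an anakinra level that the protocol's own rule has not yet passed. If the level were then rejected, the pilot's primary safety result would partly describe a regimen above the anakinra MTD.

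**Working it through.** **1. Check the plan's own figure.** Table 7 gives the probability of passing a level. With p the true DLT rate, P(pass) = (1−p)³ + 3p(1−p)²·(1−p)³. This gives 90.6%, 81.4%, 70.9%, 49.4% and 30.9% at p = 0.10, 0.15, 0.20, 0.30 and 0.40. Table 7 prints 91, 81, 71, 49 and 31%, so its reading of Table 6 is confirmed.

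**2. Compare the status with the rule.** Inputs: 2 subjects and 0 DLTs (11B1); at least 3 subjects needed (Table 6). The level is one subject short at best. Zero of 2 is also weak evidence: its probability is (1−p)², which is 64% at p = 0.20 and 49% at p = 0.30.

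**3. Chance that the level still fails.** Assume that both enrolled subjects complete follow-up without a DLT, and that Table 6 serves as the clearance test at the top level. Failure then needs a DLT in the third subject and at least one in the next three: P(fail given 0 of 2) = p[1 − (1−p)³].

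| Assumed p | Calculation | P(fail) |
|---|---|---|
| 0.10 | 0.10 × (1 − 0.729) | 2.7% |
| 0.15 | 0.15 × (1 − 0.614) | 5.8% |
| 0.20 | 0.20 × (1 − 0.512) | 9.8% |
| 0.30 | 0.30 × (1 − 0.343) | 19.7% |
| 0.40 | 0.40 × (1 − 0.216) | 31.4% |

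The rates are Table 7's grid. The true rate is unknown.

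**4. Length of the wait.** One more subject is enough with probability 1−p; otherwise 1 + 3 = 4 are needed.
- Observed pace: 2 subjects from 10 February to some day in August 2017, which is 5.65 to 6.64 months. One more subject takes 2.8 to 3.3 months and four take 11.3 to 13.3 months. This assumes that the level was open throughout.
- Planned maximum of 2 per month (11A1): 0.5 month for one subject, 2 months for four.
- Add 2 to 6 weeks of follow-up in each case.

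**5. Pilot children who could start during the wait.** 11A2 plans 10 subjects in 5 years: 10/60 per month, or one per 6 months. If the pilot opened at once:
- One-subject wait at the observed pace: 2.8/6 to 3.3/6 = 0.47 to 0.55 children.
- Four-subject wait at the observed pace: 11.3/6 to 13.3/6 = 1.9 to 2.2 children.
- At the planned maximum pace: 0.5/6 = 0.08 and 2/6 = 0.33 children.

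Multiplying step 3 at p = 0.10 to 0.20 by the longest exposure gives 0.027 × 1.9 = 0.05 to 0.098 × 2.2 = 0.2 expected children at a dose later rejected.

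**6. Weight cap.** 200/8 = 25 kg, as 11B2 states. At 6 mg/kg it would be 200/6 = 33 kg.

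**The case against.** The strongest reply is that the sequence was intended and simply not written down. The pilot starts anakinra subcutaneously (12A2), a route that 5A reserves for the first dose once the MTD is known. 18B plans an anakinra-treated control group, drawing on banked samples that include those from the anakinra Phase I trial. Table 3 lists the pilot's IND amendment and IRB approval as tasks, and these may outlast the remaining cohort; its bars are not readable, so the drawn sequence cannot be judged. These signs carry weight, but none is a condition on the first dose.

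A reader might go further and infer that the plan would let a child be dosed after 8 mg/kg had been rejected. The documents do not support that as a realistic outcome. 20B allows an earlier meeting whenever safety questions arise, and does not limit these to events in the pilot. 13A sends any Phase I/IIa SAE to the manufacturer within 24 hours, with similar reporting to FDA and the IRBs. Both studies sit in one protocol. A rejection would therefore be known to those running and overseeing the pilot. The cover is not complete, because a DLT defined only by white cell count might not be an SAE.

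A reader might also infer that 8 mg/kg is suspect. Nothing reported suggests so. There were no DLTs at that level and no drug-related SAE, and Table 2 lists children under 2 given 8 mg/kg or more with nothing beyond mild local reactions. That evidence is case reports and personal communications, and the sponsor still chose to test the level formally, but it gives no support for DLT rates of 30 to 40%.

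Finally, a reader might take 12E's one-in-six wording to mean that six subjects are always needed. The same section asks for six when a DLT occurs, and Table 6 passes a level on 0 of 3. Requiring six every time would mean 11 to 13 months at the observed pace, a debatable trade-off that this point does not need.

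**Conclusion.** The gap is real but narrow: as written, the pilot's first dose need not wait for clearance of 8 mg/kg. The conclusion rests on readable text only, and overlap of the two enrolments is possible, not shown. It also rests on a dated count: the number of subjects on 7 September 2017 is not given, nor whether the 2 in August had completed follow-up. Continued accrual at 8 mg/kg would not by itself prove the level uncleared, since the Phase IIa expansion would accrue there too. The count of 2 is what shows it.

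The exposures in step 5 assume that the pilot opens immediately, so they are upper figures for each pace and fall to nil if approvals take longer than the cohort. The failure probabilities depend wholly on assumed DLT rates; the lower end of the grid fits the reported experience better, and 31.4% at a 40% rate is an outer limit. No power or sample size figure changes. This is a cheap improvement.

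**What to change.** State in 5B, 11A2 and 12A2 that the first pilot subject is dosed only after the Phase I/IIa DSMB has reviewed the 8 mg/kg cohort and found it cleared under Table 6 (0 of 3 with a DLT, or 1 of 3 followed by 0 of 3). Add that, if the level is not cleared, the pilot uses the lower declared MTD, and the 11B2 weight ceiling is either reset (33 kg at 6 mg/kg) or deliberately kept at 25 kg.

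The cost is a few sentences and no extra patients or procedures. The wait is for one subject already planned, about 3 months at the observed pace or half a month at the planned maximum, or for four if the third subject has a DLT, plus follow-up. The IND amendment and IRB approval would absorb part or all of it. If 8 mg/kg were rejected, Table 6 already calls for at least 3 more subjects at 6 mg/kg where only 3 were treated. At 2.8 to 3.3 months each, that is a further 8.5 to 10 months before the pilot could open at the lower dose.
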